3.4 Primary Study Endpoints

Overall response by PGA of skin at week 16.

3.5 Secondary Study Endpoints

Change in modified CAILS of index treatment lesion (week 0 and 16) and change in lesion count (week 0 and week 16). Change in Pruritus VAS, VRS, & NRS, (week 0 to week 2, weeks 0 to 4, weeks 4 to 8, weeks 0 to 8, weeks 8 to 12, weeks 0 to 12, weeks 12 to 16, weeks 0 to 16, weeks 16 to 20, weeks 0 to 20, weeks 0 to 24, week 20 to 24, week 0 to 28, week 24 to 28, weeks 0 to 32, week 28 to 32), change in Skindex-16 (week 0 to week 2, weeks 0 to 4, weeks 4 to 8, weeks 0 to 8, weeks 8 to 12, weeks 0 to 12, weeks 12 to 16, weeks 0 to 16, weeks 16 to 20, weeks 0 to 20, weeks 0 to 24, week 20 to 24, week 0 to 28, week 24 to 28, weeks 0 to 32, week 28 to 32), change in LPQOL (week 0 to week 2, weeks 0 to 4, weeks 4 to 8, weeks 0 to 8, weeks 8 to 12, weeks 0 to 12, weeks 12 to 16, weeks 0 to 16, weeks 16 to 20, weeks 0 to 20, weeks 0 to 24, week 20 to 24, week 0 to 28, week 24 to 28, weeks 0 to 32, week 28 to 32), change in Physician Global Assessment (PGA)of oral mucosa, and hair (week 0 to week 2, weeks 0 to 4, weeks 4 to 8, weeks 0 to 8, weeks 8 to 12, weeks 0 to 12, weeks 12 to 16, weeks 0 to 16, weeks 16 to 20, weeks 0 to 20, weeks 0 to 24, week 20 to 24, week 0 to 28, week 24 to 28, weeks 0 to 32, week 28 to 32), change in BSA (week 0 to week 2, weeks 0 to 4, weeks 4 to 8, weeks 0 to 8, weeks 8 to 12, weeks 0 to 12, weeks 12 to 16, weeks 0 to 16, weeks 16 to 20, weeks 0 to 20, weeks 0 to 24, week 20 to 24, week 0 to 28, week 24 to 28, weeks 0 to 32, week 28 to 32), change in Modified CAILS (week 0 to week 2, weeks 0 to 4, weeks 4 to 8, weeks 0 to 8, weeks 8 to 12, weeks 0 to 12, weeks 12 to 16, weeks 16 to 20, weeks 0 to 20, weeks 0 to 24, week 20 to 24, week 0 to 28, week 24 to 28, weeks 0 to 32, week 28 to 32), and change in lesion count (week 0 to week 2, weeks 0 to 4, weeks 4 to 8, weeks 0 to 8, weeks 8 to 12, weeks 0 to 12, weeks 12 to 16, weeks 16 to 20 and weeks 0 to 20, weeks 0 to 24, week 20 to 24, week 0 to 28, week 24 to 28, weeks 0 to 32, week 28 to 32).

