Objectives	To evaluate the safety and efficacy of Baricitinib (LY3009104) in cutaneous LP as assessed by the change in Physician Global Assessment (PGA) of skin, oral mucosa, and hair, Body Surface Area (BSA), Index Treatment and Control Lesion by Modified Clinical Assessment Scale of Severity for Index Lesion Signs and Symptoms (mCAILS) score, Pruritus Visual Analog Scale (VAS), Verbal Rating Scale (VRS), Pruritus Numerical Rating Scale (NRS), and Skindex-16. To predict responses through the identification of unique biomarkers of LP at week 0 and utilizing RNA sequencing on responsive and non-responsive tissue at week 2.						
Number of Subjects	12						
Diagnosis and Main Inclusion Criteria	Non-pregnant adults with cutaneous LP						
Study Product, Dose, Route, Regimen	Baricitinib (LY3009104) 2 mg orally administrated, once daily.						
Duration of Administration	Drug will be administered from Day 0 through Week 16.						
Reference therapy	Baricitinib (LY3009104) is currently being used to treat subjects with rheumatoid arthritis and under investigation for atopic dermatitis and psoriasis.						
Statistical Methodology	The statistical analysis will provide descriptive summary statistics for categorical and continuous outcomes. Categorical variables will be described by their count and proportion of occurrence while continuous, normally distributed variables will be described by their mean and standard deviation; and continuous, non-normally distributed variables will be described by their median and range						

1 Introduction

This document is a protocol for a human research study. This study will be carried out in accordance with the applicable United States government regulations and Mayo Clinic research policies and procedures.

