To determine the efficacy of Baricitinib (LY3009104) as measured by PGA of skin overall response at week 16,

Secondary Objective:

To determine the efficacy of Baricitinib (LY3009104) as measured by the change in modified CAILS score of the cutaneous index treatment (weeks 0 and 16) and changes in lesion count (week 0 and 16), the change in Pruritus VAS, VRS, & NRS, (week 0 to week 2, weeks 0 to 4, weeks 4 to 8, weeks 0 to 8, weeks 8 to 12, weeks 0 to 12, weeks 12 to 16, weeks 0 to 16, weeks 16 to 20 and weeks 0 to 20), change in Skindex-16 (week 0 to week 2, weeks 0 to 4, weeks 4 to 8, weeks 8 to 12, weeks 0 to 12, weeks 12 to 16, weeks 0 to 16, weeks 16 to 20 and weeks 0 to 20), change in Physician Global Assessment (PGA) of oral mucosa and

hair (week 0 to week 2, weeks 0 to 4, weeks 4 to 8, weeks 0 to 8, weeks 8 to 12, weeks 0 to 12, weeks 12 to 16, weeks 0 to 16, weeks 16 to 20 and weeks 0 to 20), change in BSA (week 0 to week 2, weeks 0 to 4, weeks 4 to 8, weeks 0 to 8, weeks 8 to 12, weeks 0 to 12, weeks 12 to 16, weeks 0 to 16, weeks 16 to 20 and weeks 0 to 20), change in Modified CAILS (week 0 to week 2, weeks 0 to 4, weeks 4 to 8, weeks 0 to 8, weeks 8 to 12, weeks 0 to 12, weeks 12 to 16, weeks 16 to 20 and weeks 0 to 20), and change in lesion count (week 0 to week 2, weeks 0 to 4, weeks 4 to 8, weeks 0 to 8, weeks 8 to 12, weeks 0 to 12, weeks 12 to 16, weeks 16 to 20 and weeks 0 to 20).

Exploratory Objectives:

To predict responses and examine the pharmacodynamics of treatment through the identification of unique biomarkers and transcriptomic changes of LP at week 0 and utilizing RNA sequencing on responsive and non-responsive tissue at week 2 to correlate these biomarkers with measures of global response: Modified CAILS, PGA, BSA, and lesion count.

If the patient chooses to participate in the extension, all of the objectives listed above will be observed through to week 32.

3 Study Design

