3.1 General Description

This is a single center, exploratory, open-label, single-arm design study of 12 patients. Treatment naïve and treatment refractory patients with LP will be treated Baricitinib (LY3009104). Patients who are non-responders to physician choice standard of care will undergo a washout period and will be enrolled in the study.

Multiple safety studies have been conducted with Baricitinib (LY3009104) (see Safety) and a dose of 2 mg QD is deemed safe. (Investigator's Brochure) We propose a single center, exploratory, open-label, single-arm design study of 12 patients. Treatment naïve and treatment refractory patients with LP will be treated with Baricitinib (LY3009104) for 16 weeks.

Individuals with cutaneous LP will be eligible. Individuals must have 4 lesions at baseline; however, a minimum of 8 lesions which are at least 5mm in diameter is ideal. All lesions will be annotated, photographed, and scored. The rationale for a minimum of 8 lesions is based upon the assumption of a 50% response rate at 2 weeks. With 8 lesions, there would be a less than 1% chance that all 8 lesions would resolve spontaneously. Prior treatment will be allowed; however, a washout period of 2 weeks for topical and 4 weeks for systemic agents is required. At the washout period, individuals will undergo evaluation with a PGA and BSA calculation. The indexed lesions will be photographed, measured, scored, and recorded with Modified CAILS scores as well. The Modified CAILS calculations will be used for the determination of responsive and non-responsive lesions. Additional Pruritus measures using the VRS, VAS, NRSSkindex-16, and LPQOL will be collected at that time.

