Individuals will then initiate treatment for all lesions of LP once daily and will be evaluated weekly and assessed by PGA of skin, oral mucosa, and hair, BSA, lesion count, Modified CAILS, Pruritus VRS, VAS and NRS scales, Skindex-16, and LPQOL between weeks 0-16 (see Appendix). Week 16 will be the primary endpoint. Therapy will be stopped and the individuals will be evaluated at week 20 after an observation period of 4 weeks and assessed by PGA, BSA, lesion count, mCAILS, Pruritus VRS, VAS and NRS scales, Skindex-16, and LPQOL. Laboratory and safety monitoring will occur at weeks 1, 2, 3, 4, 8, 12, 16, 20, 24, 28, and 32. 3D Photographs will be taken at weeks 0, 1, 2, 3, 4, 8, 12, 16, 20, 24, 28, and 32. Individual lesions will be circled at each visit and the exact area of each lesion will be measured. Up close photos will be taken of the disease.

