week 0 and 2. Blood collection will include the isolation at week 0, 1, 2, 3, 4, 8, 12, 16, 20, 24, 28, and 32. Blood will be drawn into 5mL vials and subsequently separated. The serum and cell pellet will be stored for future analysis. At weeks 0 and 2, an additional 5mL vial of blood will be drawn from patients who agree to provide single-cell RNA sequencing samples. For these samples, the buffy coat (containing peripheral blood mononuclear cells, PBMCs) will be isolated from whole blood, then immediately placed into cryopreservation medium and stored in a -80°C biobank freezer. Up to five skin biopsies will be taken during the study for all patients. At week 0, up to two, 3mm tissue biopsies will be taken from LP lesional skin and one biopsy will be taken from normal appearing skin for bulk RNA sequencing. The initial biopsy of lesional tissue and control will be annotated. At week 2, up to two, 3mm biopsies will be taken – one from normal appearing skin, one from lesional responsive tissue, and/or one from lesional non-responsive tissue. An additional two, 6-8mm biopsies of lesional tissue for single-cell RNA sequencing will be taken—one at week 0 and one at week 2 from patients who opt in. The week 2 biopsy will be obtained from an annotated lesion, whether responsive or non-responsive. Responsive and non-responsive lesions will be determined by the change in mCAILS between week 0 and 2. Responsive tissue will require at least 50% reduction in mCAILS while non-responsive tissue can have progression, no change, or up to a 50% reduction in mCAILS. The lesions will be chosen utilizing full body photographs taken previously at week 0. Up to 60 of the 3mm biopsy samples will be snap frozen and stored in the tissue biobank. Once completed, RNA sequencing will be performed on the tissue samples and analysis will be performed. Paired analysis of treatment responsive and refractory lesions will be made as well as treated and untreated lesions.

Tissue will be collected for bulk RNA sequencing and single cell RNA sequencing (for patients who opt in) at

Nucleic Acid Extractions: RNA will be extracted from a total of 50 µm of fresh tissue using the Qiagen FFPE RNeasy Micro extraction Kit according to manufacturer's recommendation.

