Bulk RNA Transcriptome Sequencing: RNA transcriptome sequencing will be carried out using commercially available techniques. Briefly, RNA Libraries will be created using up to 100ng of RNA as starting material using the Illumina RNA Exome Library kit according to manufacturer's recommendation. Libraries will undergo quality control for quality and quantity using the Agilent BioAnalyzer High Sensitivity Chip. Pair-End sequencing will then be carried out on the Illumina HiSeq 4000 using 101bp insert fragments.

Single-cell RNA Transcriptome Sequencing: Samples will be prepped and analyzed per single-cell RNA sequencing standard operating procedures of the University of Michigan genomics lab.

Primary and Secondary Measures:

All efficacy assessments will be performed prior to the administration of study treatment at each visit. The recommended order and the overall outline of measurements for the efficacy assessments are described below.

Efficacy measures: PGA, BSA, mCAILS, Pruritus VRS, VAS and NRS, Skindex-16, and LPQOLto determine the efficacy of Baricitinib (LY3009104) as measured by the change in Modified CAILS score of the index lesion (weeks 0 and 16) and changes in lesion count (week 0 and 16).

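### The Week 16 mCAILS endpoint rests on one index lesion with no selection rule, although several lesions per patient are scored; a per-patient mean over those lesions would be more precise and harder to steer

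*Combined protocol and SAP*

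**What the plan says.** The Week 0 to Week 16 mCAILS endpoint is worded in three ways:

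- Section 3.5: "Change in modified CAILS of index treatment lesion (week 0 and 16) and change in lesion count (week 0 and week 16".
- Section 2, secondary objective: "change in modified CAILS score of the cutaneous index treatment (weeks 0 and 16"; the noun after the last adjective is missing.
- Section 3.1, efficacy measures: "change in Modified CAILS score of the index lesion (weeks 0 and 16".

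All three are singular. No section says how many index lesions there are or how they are picked.

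The rest of the design works with several lesions. Section 3.1 asks for 4 at baseline, with 8 of at least 5 mm as the ideal, and states: "All lesions will be annotated, photographed, and scored". The same section gives mCAILS to indexed lesions (plural) and uses mCAILS change from Week 0 to Week 2, with a 50% cut-off, to class lesions as responsive or not. Supplemental 1 speaks of a composite over index lesions. Table-3 schedules mCAILS at every visit from Day 0.

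Section 7.2 offers paired Wilcoxon tests and a mixed model for the lesion over time. It does not say which lesions enter or how lesions within a patient are handled.

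Two side phrases matter for tidying up. The Study Summary lists "Index Treatment and Control Lesion by Modified Clinical Assessment Scale of Severity for Index Lesion Signs and Symptoms (mCAILS) score", and section 3.1 says "Paired analysis of treatment responsive and refractory lesions will be made as well as treated and untreated lesions". The drug is "Baricitinib (LY3009104) 2 mg orally administrated, once daily", and section 3.1 adds "Individuals will then initiate treatment for all lesions of LP once daily".

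**The concern.** As worded, the endpoint cannot be computed without a decision that the plan leaves open: which lesion. The study is open-label and single-arm, so whoever makes that decision knows the treatment, and could make it after seeing how lesions respond. If the most severe lesion is taken at baseline, its score will tend to fall without any drug effect.

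Biopsy adds a further problem. Section 3.1 takes optional 6–8 mm samples from lesional skin at Weeks 0 and 2, while a lesion may be only about 5 mm across. Nothing stops the index lesion from being the one sampled.

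The stake is precision and credibility of a secondary result. Section 7.2 says that the 12 patients serve estimation only, so a summary that discards scored lesions weakens what the study is meant to deliver.

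**Working it through.** **The plan's own lesion-level figure.** Section 3.1 justifies 8 lesions by a chance below 1% that all 8 resolve at a 50% rate. This reproduces: 0.5^8 = 0.0039, or 0.39%. It holds only if lesions in one patient are independent. With a within-patient correlation of 0.05, 0.1 or 0.2 (beta-binomial) the chance is 1.1%, 2.3% or 5.5%. With the 4 required lesions it is 0.5^4 = 6.25% even under independence. So the plan already relies on several lesions per patient, but gives no correlation between them.

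**Precision of a mean over lesions.** Inputs: m = 4 or 8 lesions (section 3.1); 12 patients (section 3.2); ρ, the correlation of mCAILS change between lesions of one patient, which is an assumption. Relative to one lesion, the variance of the patient score is

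ratio = (1 + (m − 1)ρ) / m.

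The number of single-lesion patients giving the same precision is 12 / ratio.

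| ρ | m = 4: ratio | patients | m = 8: ratio | patients |
|---|---|---|---|---|
| 0.2 | 0.400 | 30.0 | 0.300 | 40.0 |
| 0.5 | 0.625 | 19.2 | 0.563 | 21.3 |
| 0.8 | 0.850 | 14.1 | 0.825 | 14.5 |
| 0.9 | 0.925 | 13.0 | 0.912 | 13.2 |

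Example: m = 8, ρ = 0.5 gives (1 + 7 × 0.5)/8 = 4.5/8 = 0.5625, and 12/0.5625 = 21.3. Under the independence that the plan's own lesion argument assumes, ρ = 0 and the ratio would be 1/4 or 1/8. If biopsies leave only two usable lesions, the ratio at ρ = 0.5 is 1.5/2 = 0.75.

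**Confidence interval.** With 12 patients, the 95% half-width for one lesion is t(0.975, 11)/√12 = 0.64 SD of the single-lesion change. Multiplying by the square root of the ratio, for ρ from 0.2 to 0.8, gives 0.40–0.59 SD for 4 lesions and 0.35–0.58 SD for 8.

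**Regression to the mean, for illustration.** Suppose the highest-scoring lesion is taken, and the score has reliability 0.8 among lesions of one patient. Both are assumptions. The expected maximum of 4 or 8 standard normal values is 1.03 or 1.42. The apparent fall with no drug effect is then 1.03 × 0.2 = 0.21 or 1.42 × 0.2 = 0.28 of the within-patient SD between lesions. The documents do not say that the worst lesion will be chosen. The point is that nothing rules it out.

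**The case against.** **The single lesion is read from singular nouns.** Sections 3.1 and Supplemental 1 use the plural, and the Appendix describes a sum of signs over index lesions. A composite may be intended. This stands in part: the plan may not have chosen a single-lesion design on purpose. But the listed endpoint is singular. The broader mCAILS series in sections 2 and 3.5, which is not tied to an index lesion, omits the Week 0 to 16 interval. That change therefore exists only in the index-lesion form.

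**The size rests on an assumed correlation.** This stands. At 0.9 the gain is under 10%.

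**The scores may not exist for all lesions at Week 16.** This stands in part. Section 3.1 ties mCAILS explicitly only to indexed lesions, and its statement that all lesions are scored names no scale. However, telling responsive from non-responsive lesions at Week 2 already needs mCAILS on several lesions.

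**Small lesions carry little size information.** This stands. A round 5 mm lesion covers π × 0.25² ≈ 0.2 cm², inside the lowest non-zero band of the Appendix (up to 4 cm²). Shrinkage short of clearance leaves its size score unchanged.

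**Stronger readings that the documents do not support.** A reader might infer from the Study Summary that index and control lesions will be contrasted, which under an oral drug would be null by design. Two equally exposed lesions would indeed differ by zero in expectation; in simulation with 12 patients a signed-rank test rejected about 4.3% of the time. But the control lesion for mCAILS appears only in that summary, and no such contrast is listed in section 2, 3.1, 3.5 or 7. The treated-versus-untreated sentence sits in the RNA-sequencing text and can mean Week 2 against Week 0 tissue, which is not null. A reader might also infer a layout carried over from a topical trial. The documents do not say so: index lesion is part of the scale's name, Supplemental 1 traces the scale to cutaneous T-cell lymphoma, and one source cited for it is a trial of an oral drug.

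**Conclusion.** The point holds for the Week 16 mCAILS endpoint: it is worded for one lesion without a selection rule, in an open-label study that already scores several lesions per patient. A mean over 4 to 8 lesions would leave 56–63% of the variance at a correlation of 0.5, so 12 patients would carry the precision of about 19 to 21 single-lesion patients. The range is 30–85% for correlations of 0.2 to 0.8. These figures assume equal variances and one common correlation across lesions, and the documents supply neither. The case for a rule fixed in advance does not depend on the correlation.

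The consequence is limited. The endpoint is secondary, the analysis is descriptive, BSA and lesion count cover the whole body, and the primary endpoint (PGA of skin at Week 16) is untouched. The control-lesion wording is a drafting matter, not a flawed analysis.

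**What to change.** In sections 2, 3.1 and 3.5, define the endpoint as the per-patient mean change in mCAILS from Week 0 to Week 16 over all lesions given an mCAILS score on Day 0. Also state that:

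- the set of lesions is recorded before the first dose and followed unchanged;
- a lesion that has cleared scores zero and is not treated as missing;
- lesions biopsied at Day 0 or Week 2 are left out, with their number reported, and a fallback covers patients left with too few lesions;
- any single index lesion is supportive, with its selection rule given.

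Week 2 biopsy sites are chosen partly by response, so a sensitivity analysis that keeps those lesions is worthwhile. In section 7.2, analyse one value per patient, or specify a mixed model with lesions nested within patients.

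As tidy-up only, remove the control lesion from the Study Summary objectives, since an oral drug reaches every lesion. In section 3.1, say that treated and untreated lesions means Week 2 against Week 0 tissue.

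The cost is mostly wording, with no new visit or instrument. The one practical demand is that the lesions scored on Day 0 are scored with mCAILS again at Week 16, which section 3.1 now states only for indexed lesions.

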3.6 Primary Safety Endpoints

A thorough baseline screening will be followed for all patients and is outlined in Table-2. A detailed list of the methods in which baseline screening will be performed is outlined in Supplemental 2. All blood draws and safety assessments must be performed prior to study treatment administration. Appropriate safety assessments (e.g., evaluation of AEs and SAEs) should be repeated after dosing with study treatment. A physical examination, including general appearance and vital signs, will be performed as indicated in Table-2. If indicated, based on medical history and/or symptoms, additional exams will be performed at the discretion of the investigator. If possible, the same member of the study site staff throughout the study will perform assessments for an individual subject. Information for all physical examinations will be included in the source documentation at the study site. Significant findings that are present prior to the subject signing informed consent will be included in the Medical History. Significant findings made after the signing of the informed consent, which meet the definition of an AE, must be recorded as an AE. Vital signs (blood pressure, pulse, height, weight) will be assessed at each physical examination as indicated in Table-2 (see Supplemental 2 for details on how to acquire vital signs). Whether action needs to be taken to address notable vital signs will be decided by the investigator, considering the overall status of the subject. Laboratory studies will be drawn as indicated in Table-2. Whether action needs to be taken to address notable laboratory values will be decided by the investigator, considering the overall status of the subject. Hematology assessments will be measured at all scheduled study visits specified in Table-2. Serum chemistry will be a comprehensive metabolic and lipid panels that will be measured at all scheduled study visits specified in Table-2.

If the prohibited treatment is being used during the study for any indication, the subject must discontinue use of the prohibited treatment if he/she wishes to continue in the study. In case of undue safety risk for the subject, the subject should discontinue study treatment at the discretion of the investigator/qualified site staff. If the subject received a live virus vaccination during the study, the subject must discontinue study treatment.

3.7 Identification of Source Data

All data in the study will be captured in the case report forms including:

- Safety measures
- Efficacy measures
- Laboratory studies
- Vital Signs
- Exploratory measures

4 Subject Selection Enrollment and Withdrawal

4.1 Inclusion Criteria

Subjects eligible for inclusion in this study must fulfill all the following criteria:

- Subjects must be able to understand and comply with the requirements of the study and communicate with the investigator. Subjects must give written, signed, and dated informed consent before any study related activity is performed. When appropriate, a legal representative will sign the informed consent according to local laws and regulation
- Both men and women must be at least 18 years of age at the time of screening
- Subjects must have clinical and histological features of LP
- LP requiring systemic treatment
- Subjects must have treatment naïve cutaneous LP or treatment refractory disease, as defined by failure of at least one established treatment for LP
 - o Failure of prior therapy
 - Topical treatment
 - Systemic immunosuppressant
 - Oral metronidazole
 - Oral sulfasalazine
 - Oral retinoid

